2.2 Study Rationale

Using antipsychotic medications to control agitation and aggression among people with ADRD increases the risk of complications, (11) including extrapyramidal symptoms, (12, 14) serious cardiovascular events, (14, 15, 49-51) and even death.(16)(17, 18, 20) For this reason, existing guidelines recommend exhausting nonpharmacological options; (20, 21) indeed, decreasing the use of antipsychotics for NH residents with ADRD is a CMS goal. (22) Unfortunately, as ADRD progresses, behavioral symptoms, including agitation and aggression, worsen, perhaps due to an inability to modulate responses as a direct effect of damage to the brain as well as sensory deprivation that can induce fear, anxiety, and confusion. (52-55) Eliciting musical memories using familiar music may decrease feelings of isolation and anxiety(23, 24) since musical memories are encoded in areas of the brain affected later than are areas of the brain governing verbal memory and executive functioning.(25-29) Individualized music has been shown to reduce anxiety.(30-32) decrease negative affect or depression, (30, 31) and to control physically agitated behaviors (33, 34) in people with ADRD. Further supporting the neurological pathway of eliciting musical memory, individualized music selections are more effective at reducing agitation compared to playing "relaxing" or classical music.(56) Several systematic reviews highlight the potential for music therapy to reduce agitation. (57-60) aggression. (58) anxiety. (61) behavioral symptoms, (61, 62) and mood. (62) This proposed pragmatic trial will **not** test the neurological premise on which individualized music is based, which would require complex imaging studies along with detailed behavioral monitoring. Rather, its significant contribution is testing the effectiveness of individualized music as a non-pharmacological treatment for BPSD.

MUSIC & MEMORY (M&M) is a music program that builds upon an evidence-based protocol(63) by using easily-operated iPods to deliver individualized music to people with ADRD. The program was developed by a social worker, [name], with experience leveraging technology to benefit those who would otherwise have no access. Caregivers (providers, family, or others) provide cognitively-impaired people with music playlists tailored to their personal history of music preferences.(35) The program assumes that musical memories remain present and that personalized music can guell the anxiety and agitation stimulated by the confusion secondary to brain disease. Its potential is illustrated powerfully in the 2014 documentary, Alive Inside, which shows people with severe dementia begin to move, sing, and even describe memories.(64) Thousands of provider sites across the world have become certified in M&M, including hundreds of NHs in the U.S. NH staff participate in MUSIC & MEMORY, Inc.-led certification and training webinars that offer suggestions for choosing residents to receive iPods, identifying music preferences, and sustaining the use of the iPods. The M&M website offers materials and ongoing support to participating facilities. Twelve states have M&M NH demonstration projects underway. However, to date demonstration evaluations have revealed wide variation in the level, approach and sustainability of implementation of M&M. For example, there has been variation in which residents receive an iPod, where the iPods are stored, and how often residents have access to them.(65) Rigorous evaluation of a uniformly-implemented intervention is necessary to definitively establish the program's efficacy and to characterize factors associated with effective implementation.

3 STUDY DESIGN

We will conduct two parallel, cluster RCTs of M&M for people with ADRD in 81 NHs; the unit of random assignment will be the facility and the unit of analysis the resident, clustered within the facility (see Table 1, next page). The primary study outcome is agitated and aggressive behaviors, as measured by interviewing a staff member who knows the resident well. Secondary study outcomes include: agitated and aggressive behaviors measured through direct observation of the resident when s/he is using and not using the music, agitated and aggressive behaviors as reported in available administrative data, emotional states observed while the resident is using and not using the music, antipsychotic use, antidepressant use, anti-anxiolytic use, and depression. First, using MDS data obtained from each corporation's EHR and centralized corporate knowledge about their facilities' capabilities and constraints, we will identify eligible facilities and contact facility

leadership to ensure that they want to, and have the necessary staffing resources to participate. Second, stratifying by corporation and prevalence and balancing on other key study variables at baseline, we will randomize facilities within corporation to one of three intervention waves. Third, we will use the most recent MDS data to identify eligible residents within each facility from the pool of long-stay residents with ADRD. At the same time, we will use knowledge gained from the R21 pilot phase to develop train-the-trainer materials and make any needed revisions to the step-by-step protocol. Fourth, we will train corporate trainers and support them as they train staff in participating facilities and mentor sites during implementation. Finally, we will obtain primary and secondary data for evaluation, using Research Assistant (RA) obtained observation and data from NHs' EHRs, merged with MDS and Medicare enrollment records. Obtaining, merging, and cleaning these data will occur throughout implementation phase.

Tuble I. Repeat I dialle			
	Period 1	Period 2	Period 3
	(June, 2019 -	(April, 2020 -	(February 2021 -
	January, 2020)	November, 2020)	September, 2021)
Sequence 1	Intervention**	Coronavirus	Intervention ⁺
(27 Nursing Homes)	(405 residents)	Pandemic†	(405 residents)
Sequence 2	Control*†	Coronavirus	Intervention*†
(27 Nursing Homes)	(405 residents)	Pandemic†	(405 residents)
Sequence 3	Control†	Coronavirus	Control*†
(27 Nursing Homes)	(405 residents)	Pandemic†	(405 residents

Table 1. Repeat Parallel Design

*Primary data collection conducted in Sequence 1 and Sequence 2 nursing homes during Period 1, and Sequence 2 and Sequence 3 nursing homes during Period 3

[figure not shown]
*Secondary data collection including Minimum Data Set (MDS) and medication order data collected in all periods for all sequences, even during the coronavirus.

4 SELECTION AND ENROLLMENT OF PARTICIPANTS

4.1 Resident Inclusion & Exclusion Criteria

Eligible residents must be long-stay and have ADRD. Long-stay residents include anyone who had a quarter or annual assessment in the past four months. ADRD is defined by the presence of a dementia diagnosis and either a Brief Interview for Mental Status score ≤12 or moderately or severely daily decision-making. Resident exclusion criteria include being deaf or not liking music. Figure 2 describes the process for identifying eligible residents using Minimum Data Set (MDS) data.

Figure 2. Steps for Identifying Eligible Residents Using the Minimum Data Set

4.2 Facility Inclusion & Exclusion Criteria

Using the Minimum Data Set (MDS), Brown will identify facilities which have at least 15 eligible residents. Brown staff will provide a list of facilities who are likely to have enough residents meeting eligible criteria to corporate leadership. From the list of potentially eligible facilities, corporate leadership will eliminate any facing other significant threats to implementation (e.g., recent leadership changes, recent poor regulatory survey performance such as immediate jeopardy or monetary penalties). Corporate leadership will reach out to potentially eligible facilities to allow for an opt-out of participation and to verify that they are not currently using M&M.

4.3 Study Enrollment Procedures

4.3.1 Facility Recruitment Procedures:

Once eligible facilities are identified, they will be contacted by the Brown project leadership for a baseline telephone interview. The purpose of this call is to describe the study and provide a final opportunity for the facility to opt-out, without corporate leadership present. While senior corporate leaders strongly endorse the project, the final decision to participate in the intervention arm will be the individual facility's administrator.

Once the NHs are recruited, they will be randomly assigned (*see Section 4.3.3. for randomization procedures*) to one of three intervention waves by Brown statisticians.

4.3.2 Facility Recruitment Estimates:

Based upon our sample size calculations (*see Section 9.2*), we require 24 facilities per arm (72 facilities total). To account for the fact that some facilities may not successfully implement the intervention post-randomization, we increased our facility recruitment targets to 27 facilities in each study arm (81 facilities total) Table 2 provides the key characteristics of eligible facilities by corporation.

	Corporations				
	Α	В	С	D	
Eligible Nursing Homes (#)	69	12	25	76	
Geographic Region	Mid-West	Mid-West	Mid-Atlantic	South	
Black Residents (%)	1%	<1%	53%	42%	
CMS Overall Quality Star Rating (Mean)	3.4	4.5	2.0	3.1	
Ownership Type	Non-Profit	Non-Profit	For-Profit	For-Profit	
Residents with any antipsychotic Use in Last 7 days (%)	23%	18%	25%	26%	
Residents with any agitated or aggressive behaviors (%)	27%	14%	15%	17%	

Table 2. Key Characteristics of Eligible Nursing Homes by Partnering Corporation

4.3.3 Facility Randomization and Stratification Procedures:

Facilities will be randomized within NH health care system strata. Within each health system, sites will be partitioned into triplets based on the Mahalanobis distance from the overall mean on the following key variables: percentage of eligible nursing home residents with any agitated or aggressive behavior (MDS Aggressive Behavior Scale > 0) on their most recent quarterly or annual assessment and number of eligible long-stay residents. The rationale for this additional balancing is that agitated and aggressive behaviors, a study outcome of interest, are known to vary considerably at the facility-level due to nursing home resident composition, staffing, and the degree of "ascertainment" and documentation of behaviors. It was also important to balance on the number of eligible residents in a nursing home, because nursing homes with more eligible residents can be more selective in who receives the program, possibly picking "better" candidates. Within balanced triplets, one facility will be randomly chosen for each of three periods (Table 1).

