Aim 2 of this study is to estimate the impact of M&M on agitated and aggressive behaviors in NH residents with moderate to severe dementia. Agitated and/or aggressive behaviors are measured three ways: by interviewing staff about resident behaviors over time (primary outcome); through direct observation of residents when using and not using M&M (secondary outcome); and using available administrative data (secondary outcome). Other secondary outcomes include: other emotional states directly observed while the resident is using and not using M&M (anger, pleasure, alertness, sadness), antipsychotic use, antidepressant use, anxiolytic use, and depression. In this cluster RCT, the unit of random assignment is the facility, but the unit of analysis is the patient, clustered within the facility. The analytic approach we propose is based upon the cumulative likelihood of reductions in agitated and aggressive behaviors in a long-stay population with moderate to severe dementia, conditional upon survival to at least one post-intervention observation. Outcomes will be evaluated using a repeat parallel design, comparing wave 1 (intervention) and wave 2 (control) NHs (n=54) in the first study year, and wave 2 (intervention) and wave 3 (control) NHs (n=54) in the second study year. The repeat design allows for modification of the intervention delivery between waves to increase adherence. Since we do not expect the intervention to affect mortality, the comparison will be based on the last observed total agitation score among residents meeting eligibility criteria in the treated and control groups. All deaths among exposed and control populations will be routinely controlled and reported to the data safety and monitoring board for monitoring purposes. Facilities will be stratified by corporation, and balanced on baseline agitated and aggressive behaviors and number of eligible residents, prior randomization. Because we are interested in the effect of the intervention among those who use it, we will also conduct an as-treated analysis, using a technique described by multilevel-mixture analysis for analyzing cluster randomized data with non-compliance.

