9.4 Outcomes

9.4.1 Primary outcome

The primary outcome for this study is the frequency of agitated and aggressive behaviors, as measured by the CMAI. The CMAI has 29 items organized under three domains: aggressive behavior, physically nonaggressive behavior, and verbally agitated behavior.(83) For each item, a staff member familiar with the resident's behavior is asked how often each behavior occurred in the past week. Response choices are: never (1); less than once a week (2); once or twice a week (3); several times a week (4); once or twice a day (5) several times a day (6); or several times an hour (7). For NH residents with dementia the inter-observer reliability of the CMAI was: .62 for physically aggressive behaviors (reliable change index, RCI = 7.54), .73 for physically non-aggressive behaviors (RCI = 7.09), and .61 for verbally agitated behaviors (RCI = 5.80).(87)

Test-retest reliability was: .82 for physically aggressive behaviors (reliable change index, RCI = 2.59), .83 for physically non-aggressive behaviors (RCI = 5.44), and .86 for verbally agitated behaviors (RCI = 3.22).(87) During the R21 phase, the average total CMAI score for eligible residents at baseline was 60.98 (SD:15.37). Average total CMAI scores were similar across nursing home corporations (Table 3).

	Obs	Mean	SD	Min	Max	Kurtosis
Overall	42	60.98	15.37	30	95	2.41
Good Sam	10	63.90	20.23	38	95	1.65
Vetter	12	59.58	13.79	38	89	3.10
Pruitt	10	58.20	10.35	42	77	2.39
CommuniCare	10	62.50	17.44	30	86	2.44

9.4.2. Secondary Outcomes:

Secondary outcomes are obtained from primary and secondary data sources.

Primary Data

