9.5 Data Analyses

The analytic approach in the second parallel trial is based on the minimum observed frequency of agitated and aggressive behaviors after intended exposure to the intervention (treatment) or after 8-months (control), conditional upon survival to at least one post-intervention observation (up to 4 months after baseline measurement). Our primary analysis is based upon an intent-to-treat principle, and we estimate complier average causal effect as a secondary analysis. The compliers analysis estimates the effects of the intervention for residents who received the music or would have received the music.

Our primary ITT analysis model is based on the model described by Murray & Blistein (2003) and Teerenstra et al (2012). Let Y_{ijk} be the staff interview for resident $i \in \{1, ..., n\}$ from NH $j \in \{1, ..., J\}$ at time $k \in \{baseline, post - exposure\}$, I_{ij} be an indicator that is equal to 1 if resident i in facility j is in the treatment group and T_{ij} is an indicator that is equal to 1 if this is the baseline score for resident i in facility j. We assume that $Y_{ijk} = \mu_{ijk} + \epsilon_{ijk}$, where $\epsilon_{ijk} \sim N(0, \sigma_{\epsilon}^2)$, and $\mu_{ijk} = \mu + \gamma T_{ij}I_{ij} + \tau(1 - T_{ij})(1 - I_{ij}) + \alpha(1 - T_{ij})I_{ij} + u_j + (u\tau)_{j,k} + s_{ij}$. We define $u_j \sim N(0, \sigma_u^2)$ as the deviation of cluster j from the overall mean, $(u\tau)_{j,k} \sim N(0, \sigma_{u\tau}^2)$ represent the variation of each cluster at different time points, $s_{ij} \sim N(0, \sigma_s^2)$ is the variation of individuals, γ is the difference at baseline between the mean of the intervention and control clusters, τ is the change from baseline to follow-up of the control clusters means, and α is the conditional treatment effect. Individual level covariates comprise of baseline variables including baseline CMAI. The estimate of interest would be the difference in marginal means.

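### The primary ITT model has no corporation term although homes are randomised within corporation; the cost is some precision, not bias

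*Combined protocol and SAP*

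**What the plan says.** Section 4.3.3 sets the allocation: "Facilities will be randomized within NH health care system strata". Within each corporation, "sites will be partitioned into triplets based on the Mahalanobis distance from the overall mean on the following key variables", namely facility agitation prevalence and number of eligible residents. Within a triplet, "one facility will be randomly chosen for each of three periods". The Précis agrees: "Facilities will be stratified by corporation, and balanced on baseline agitated and aggressive behaviors and number of eligible residents, prior randomization". Section 3 words it a little differently, "stratifying by corporation and prevalence and balancing on other key study variables at baseline", but it also names corporation as a stratum.

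Section 9.5 gives the primary model. It has arm-by-time terms (γ, τ, α) and random effects for home, home-by-time and resident. The home effect is a deviation from the overall mean, not from a corporation mean. On covariates it says only: "Individual level covariates comprise of baseline variables including baseline CMAI". Section 9.5 does not mention corporation, stratum or triplet, and the complier model leaves its covariates unnamed. The estimate of interest is a difference in marginal means, not defined further.

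**The concern.** Corporation is balanced across the arms by design, so differences between corporations cannot add to the error of the arm comparison. The written model nevertheless leaves any such differences in the home random effect, and so in the standard error. The result can be a test run below its nominal 5% and some power given away. There is also a pre-specification point: an analyst who adds the stratification factor and one who follows section 9.5 literally would fit different primary models.

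**Working it through.** **Inputs.** Section 9.2: SD 20, ICC 0.12, correlation of baseline and follow-up home means 0.5, difference 6 points, alpha 0.05 (two-tailed per the Précis), power 80%, 27 homes per arm recruited. Section 9.2 gives no value for residents per home; 15 is the eligibility minimum and equals 405/27 in Table 1. Assumed, because the documents give neither: 27 homes per arm split 10/4/4/9 over the four corporations, and the share of between-home CMAI variance due to corporation. Corporation effects are taken as equal at baseline and follow-up.

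**Step 1: the plan's own figure.** 2(1.96 + 0.8416)² × 400/36 × (1 + 14 × 0.12) × (1 − 0.25) = 174.4 × 2.68 × 0.75 = 350.6 residents per arm. Divided by 15 this is 23.37, so 24 homes, as stated. The formula has no stratification factor, so this point does not disturb it.

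**Step 2: variances of home means.** Total: 0.12 × 400 + 0.88 × 400/15 = 48 + 23.47 = 71.47. Baseline to follow-up covariance: 0.5 × 71.47 = 35.73. A 30% share is 0.30 × 48 = 14.4. Within corporation the variance is then 57.07, the covariance 21.33 and the correlation 0.374.

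**Step 3: three readings of the contrast.** In the section 9.5 parameters the follow-up difference is α − τ and the difference in change is α − τ − γ. The third reading is the follow-up difference adjusted for baseline CMAI. Each standard error is √(2v/27).

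| Contrast | v assumed by model without term | True v of that contrast | v with term |
|---|---|---|---|
| Follow-up only | 71.47 | 57.07 | 57.07 |
| Baseline-adjusted | 0.75 × 71.47 = 53.60 | 1.25 × 57.07 − 21.33 = 50.00 | 57.07 × (1 − 0.374²) = 49.09 |
| Change from baseline | 2(71.47 − 35.73) = 71.47 | 2(57.07 − 21.33) = 71.47 | 71.47 |

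Without the term, the effective critical value is 1.96 × √(assumed/true). That is 2.19 for follow-up only (type I error 2.8%) and 2.03 for the baseline-adjusted contrast (4.2%). For change from baseline it stays at 1.96, because stable corporation differences cancel.

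**Step 4: simulation with t-tests at home level, 30% share.**

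| Contrast | Power without / with | Type I error without / with |
|---|---|---|
| Baseline-adjusted | 84.1% / 86.5% | 4.1% / 4.9% |
| Change from baseline | about 72% / 72% | about 5% / 5% |
| Follow-up only | 74.7% / 81.9% | 2.8% / 5.0% |

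For the baseline-adjusted contrast at smaller shares, averaged over three assumed splits that agreed within 0.4 points, power without and with the term is 83.3% and 83.1% at 0%, 83.5% and 83.9% at 10%, and 83.9% and 85.1% at 20%.

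**Step 5: what the documents say about the share.** Section 9.4.1 reports: "Average total CMAI scores were similar across nursing home corporations". From Table 3, the between-corporation mean square is 69.7 and the within-corporation mean square 249.4, so F(3,38) = 0.28, p = 0.84, and the variance component is estimated below zero. But a 30% share of between-home variance is only 0.30 × 0.12 = 3.6% of total variance. With 42 residents the pilot has about 12% power to detect that, and its upper 95% limit (ignoring clustering within homes) is about 22% of total variance. In Table 2, the row "Residents with any agitated or aggressive behaviors" shows 27% in one corporation and 14% to 17% in the others. This is MDS agitation, not CMAI, and the documents give no between-home SD from which to turn it into a share.

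**The case against.** The strongest reply is that the gain may be nil. If the difference in marginal means is a change from baseline, stable corporation differences cancel and the term does nothing. That stands, and it is why the size is given by contrast. The follow-up-only reading, where the gain is largest, is the least natural one, since baseline CMAI is a named covariate.

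Second, the only CMAI evidence points to no corporation difference. This is correct as far as it goes, but 42 residents cannot exclude a share that matters. A reader might infer from Table 2 that CMAI must differ by corporation. The documents do not support this: section 9.2 chose CMAI because the MDS under-ascertains agitation, section 4.3.3 attributes facility variation partly to documentation, and Table 2 describes the eligible homes, not the 81 randomised.

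Third, homes are randomised within triplets, so a corporation term alone does not fully mirror the allocation. This also stands. Fitting all 27 triplets would take 26 indicators out of about 52 degrees of freedom. Corporation alone is an efficiency choice and should be described as one.

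Fourth, equal numbers per corporation in each arm is inferred from the triplets. The documents do not give the counts or say what happens if a count is not divisible by three.

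A reader might also expect a larger gain, from 88.0% to 92.1% power at a 30% share. That follows from removing the full 14.4 while keeping the correlation at 0.5 within corporation. If the 0.5 describes all homes together and corporation effects are stable, the correlation falls to 0.374 and baseline CMAI has already absorbed part of the gain.

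**Conclusion.** The omission is real: corporation is a randomisation stratum, it is absent from the primary model, and a sentence about individual-level covariates does not supply a facility-level factor. The consequence is limited. A reader might infer a biased estimate, inflated type I error or a wrong sample size. None follows: corporation is balanced across arms, any error in the standard error makes the test conservative, and the 24 homes reproduce.

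At an assumed 30% share the gain in power is about 2 points for a baseline-adjusted contrast, none for change from baseline and about 7 points for follow-up only. At a zero share the term changes power by about 0.1 to 0.2 points. These figures rest on the assumed share and split, on stable corporation effects, and on a home-level analysis standing in for the section 9.5 mixed model. This is an inexpensive improvement worth considering, not a flaw that threatens the result.

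**What to change.** In section 9.5, pre-specify corporation as a fixed effect (three indicators) in the primary ITT model, and state which contrast the difference in marginal means denotes. The data are already held, so the change is wording only. The price is 3 of about 52 home-level degrees of freedom.

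Optionally, report a sensitivity analysis that adds facility agitation prevalence and number of eligible residents. Triplets formed on distance from the mean may balance these only weakly, because distance does not distinguish high from low. They are better kept out of the primary model: if they explain nothing, adding them costs about 1.6 points of power (83.1% to 81.5%).

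### Triplets formed on distance from the overall mean do not match homes on agitation prevalence or size, so they add little protection against chance imbalance beyond corporation strata, and the primary model names neither variable

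*Combined protocol and SAP*

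**What the plan says.** Section 4.3.3 sets the allocation. "Facilities will be randomized within NH health care system strata". Inside each health system, "sites will be partitioned into triplets based on the Mahalanobis distance from the overall mean on the following key variables": the percentage of eligible residents with an MDS Aggressive Behavior Scale score above zero, and the number of eligible long-stay residents. One home per triplet is then drawn at random for each of the three sequences, and the section calls the triplets balanced.

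The section explains why both variables matter. Behaviors vary between homes through case mix, staffing and how fully they are documented. On size it says "It was also important to balance on the number of eligible residents in a nursing home", because homes with a larger pool can be more selective about who gets the music.

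Two other places describe the same step. The Précis (Design and Outcomes, Aim 2) says facilities will be "balanced on baseline agitated and aggressive behaviors and number of eligible residents, prior randomization". Section 3 describes "stratifying by corporation and prevalence and balancing on other key study variables at baseline".

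On adjustment, Section 9.5 says "Individual level covariates comprise of baseline variables including baseline CMAI". The displayed primary model has a baseline arm difference, follow-up terms, and random effects for home, home by time, and resident. It shows no term for corporation, triplet, prevalence or number of eligible residents.

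**The concern.** Distance from a mean is one unsigned number per home. Homes that share it lie on the same ellipse around the mean but may sit on opposite sides of it. Balance on the two variables needs homes within a triplet to be close to each other, which is a home-to-home distance. The text gives no signed score, home-to-home distance, balance check or re-randomization rule.

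If the rule was applied as written, most of the additional balancing the plan relies on is not delivered, and the Précis and Section 4.3.3 claim more than the procedure provides. The backstop is incomplete, since the model does not name either variable. Section 3 also describes stratification by prevalence, which Section 4.3.3 does not do. A reader cannot tell from the documents which scheme produced the allocation.

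**Working it through.** **The plan's own figure.** Section 9.2, with SD 20, ICC 0.12, r = 0.5, a 6-point difference, two-sided alpha 0.05, 80% power and 15 residents per home (405/27 in Table 1):

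n_res = 2 × (1.960 + 0.842)² × 400/36 × (1 + 14 × 0.12) × (1 − 0.25) = 350.6 per arm; 350.6/15 = 23.4, so 24 homes.

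The stated 24 is reproduced (power about 81% with 24 homes, 85% with 27). It takes no credit for matching, so this point does not affect it.

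**Why the rule does not match.** With uncorrelated covariates in SD units, squared distance is (prevalence)² + (size)². Homes at (+1, 0), (−1, 0) and (0, +1) all have squared distance 1 and can form a triplet, although two of them are 2 SD apart on prevalence.

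**What this does to balance.** With 27 triplets and one home per arm from each, the variance of the difference between two arm means, in covariate SD units, is (2/27) × w. Here w is within-triplet variance as a share of within-corporation variance.

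- Corporation strata only: w = 1, SD = √(2/27) = 0.272.
- Good matching: w ≈ 0.255, SD = 0.272 × √0.255 = 0.137.

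The rule's own w was found by simulation: 81 homes, 2,000 replicates. Inputs from the documents are 27 homes per arm and four corporations with mean prevalence 27%, 14%, 15% and 17% (Table 2). Assumed: 30, 6, 12 and 33 homes per corporation (roughly proportional to 69, 12, 25 and 76 eligible, in multiples of three); the two variables independent; within-corporation spread either normal (SD 8 percentage points for prevalence; mean 40, SD 12 for eligible residents) or skewed (beta for prevalence, shifted gamma for residents). *Overall mean* was read both ways, as the corporation's mean and as the mean of all homes.

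Results are given as prevalence / number of eligible residents. The first two result columns are the SD of the arm difference in covariate SD units.

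| Rule | Normal | Skewed | Chance of a difference above 0.25 SD |
|---|---|---|---|
| Corporation strata only | 0.278 / 0.279 | 0.269 / 0.276 | 35–37% / 37–38% |
| Distance from corporation mean | 0.279 / 0.269 | 0.270 / 0.249 | 34–38% / 33–36% |
| Distance from all-home mean | 0.242 / 0.277 | 0.248 / 0.244 | 31–32% / 29–37% |
| Home-to-home distance | 0.140 / 0.139 | 0.138 / 0.142 | 7% / 8% |

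Within-triplet variance share w:

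- Distance from corporation mean: 0.96–1.04 (prevalence), 0.84–1.04 (residents).
- Distance from all-home mean: 0.80–0.81 and 0.78–1.01.
- Home-to-home: 0.25–0.27 on both.

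The rule therefore removes 0 to about 20% of the variance on prevalence and 0 to about 22% on size, against about 75% for true matching. A repeat of the normal case agreed to about 0.01, with 0.13 on both variables for home-to-home matching. In it, 79% of triplets contained homes on both sides of the corporation's mean prevalence (61% under the all-home reading), against 78% for random triplets. The mean arm difference was about zero under every rule.

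**The case against.** The strongest reply has five parts.

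1. *Randomization is intact.* A reader might infer that the arms are unbalanced or the comparison biased. The documents do not support that. Drawing one home per sequence at random is unbiased for any triplets, and realized balance is unknown. What is weakened is protection against chance. This stands.
2. *The wording may be looser than the procedure.* It could be shorthand for home-to-home matching. If *overall mean* is the all-home mean, the distance also carries some direction, because one corporation is at 27% and the others at 14–17%; the SD for prevalence then falls from 0.278 to 0.242 in the normal case. This stands as an uncertainty. The gain is modest, and the written rule is what a reader would replicate.
3. *The model already adjusts.* A reader might infer that an imbalance passes straight into the treatment contrast. For agitation it does not: baseline CMAI is in the model and is the outcome scale itself, whereas Section 9.2 says the MDS under-ascertains agitation. The covariate list is also open-ended. This stands in part, but neither home-level variable is named, and baseline CMAI does not address home size directly.
4. *The effect on the outcome scale is probably small.* Between-home SD is 20 × √0.12 = 6.9 CMAI points. A 0.25 SD imbalance moves the contrast by 0.25 × 6.9 = 1.7 points times the home-level covariate-outcome correlation, which the documents do not give. For assumed correlations of 0.1 to 0.5 that is 0.2 to 0.9 points before baseline adjustment. The standard error implied by Section 9.2 with 27 homes per arm is √(2 × 400 × 2.68 × 0.75 / 405) = 2.0, and the target is 6 points. Residual chance imbalance is part of the between-home variance and so of that standard error; it does not inflate type I error. This stands.
5. *The remedy is partly there.* Section 9.2.3 already promises aggregated baseline comparisons of the arms. A main-effect term for size also does not undo selection of residents within larger homes. Both stand.

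**Conclusion.** The point holds in a limited form. As written, the triplets are not matched on either variable and give an SD of the arm difference of about 0.24 to 0.28 covariate SD. Corporation strata alone give about 0.27 to 0.28, and home-to-home matching about 0.13 to 0.14. The claim of balance in the Précis and Section 4.3.3 is therefore largely unsupported by the stated procedure, and Section 3 describes a different one.

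The loss is in precision and protection against chance; validity and the 24-home calculation are unaffected. That distance from a mean is unsigned needs no assumption. The sizes rest on assumed home counts per corporation, assumed spreads and independent covariates, and on the written rule being the one that was used. The documents settle neither that last point nor the realized balance.

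**What to change.** 1. Add the percentage of eligible residents with an Aggressive Behavior Scale score above zero, and the number of eligible long-stay residents, as prespecified home-level fixed covariates in the primary intention-to-treat model of each trial. For Trial 2, take both from the last MDS extract before Period 3. Homes are randomized once to all three waves, and Period 3 starts in February 2021, 20 months after Period 1 began, so values used at allocation will be out of date.
2. State in Section 4.3.3 whether distance from the mean or home-to-home distance was actually used, and which mean. If it was distance from the mean, drop or qualify the balance wording there and in the Précis.
3. Reconcile Section 3 with Section 4.3.3, and name both variables in the baseline comparison planned in Section 9.2.3.

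The cost is some wording and two model terms, about two degrees of freedom out of the 54 homes in each trial. The MDS data are already collected for all sequences and periods (Table 1 footnote), so no new data and no re-randomization are needed.
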